## **Intervention**

Home-Based Exercise Program: Walking or cycling for 5–10 minutes once or multiple times daily; Gradually increasing duration by 3–5 minutes until reaching 30–60 minutes per session; Exercise 2–3 days per week initially, progressing to 4–7 days per week; Performed on non-dialysis days.

## **Data Collection Tools and Methods**

Depression Assessment: PHQ-9 questionnaire (University of Michigan Depression Center).

Anxiety Assessment: GAD-7 questionnaire (University of Michigan Depression Center).

Data will be collected via face-to-face interviews and patient medical records from the Al Shifa system.

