## **Study Design**

This research will be conducted in two main phases:

Phase I: Cross-sectional study to assess baseline levels of depression and anxiety using validated tools.

Phase II: Randomized controlled trial (RCT) with two groups:

- Intervention Group: Receives structured, home-based walking exercise program for 6 months.
- Control Group: Receives standard care without exercise intervention.

Post-intervention assessment will be conducted for both groups after 6 months using the same tools.

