### **Expected Outcomes**

The intervention group is expected to show a statistically significant reduction in depression and anxiety scores compared to the control group, supporting the integration of home-based exercise programs in dialysis care.

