The Effect of Non-Pharmacological (Home-Based Exercise) Intervention on Psychological Distress of Patients Undergoing Hemodialysis at Al Suwaiq Renal Dialysis Center

NCT07083843

Date:15/08/24

Study Objectives

Primary Objective: To evaluate the effect of home-based exercise on reducing psychological distress (depression and anxiety) in patients undergoing hemodialysis.

Secondary Objective: To describe the baseline prevalence and severity of depression and anxiety among hemodialysis patients.

Study Design

Phase I: Cross-sectional assessment of depression and anxiety levels using the University of Michigan Depression Center's tools.

Phase II: Randomized controlled trial (RCT) with intervention and control groups.

Phase III: Post-intervention reassessment after 6 months.

Study Population

Sample size: Initially 132 screened → 54 enrolled → 26 participants per group in final analysis.

Inclusion/Exclusion Criteria: As defined in the study protocol.

Variables

Primary Outcomes: Depression Score (0-27) using PHQ-9 scoring; Anxiety Score (0-21) using GAD-7 scoring.

Independent Variable: Intervention group assignment (Home-based exercise vs. Control).

Covariates: Age, gender, duration of dialysis, comorbidities.

Data Collection Method

Face-to-face interviews for questionnaire administration. Baseline data from Al Shifa system (demographics, clinical history).

Statistical Analysis

- Data Management: Data entry and cleaning in SPSS v22. Descriptive statistics for demographics and baseline variables: Continuous variables: Mean ± SD (or median and IQR if non-normal). Categorical variables: Frequencies and percentages.
- Baseline Comparisons: Independent t-test, Chi-square, or Fisher's exact test for categorical variables.

Main Analysis: Paired t-test for within-group changes; Independent t-test for between-group differences in change scores.

- Significance Level: p-value < 0.05 considered significant; two-tailed tests.

- Handling Missing Data: Intention-to-treat principle; Last Observation Carried Forward method for missing values.

Presentation of Results

Tables for baseline demographics, pre- and post-intervention scores. Paired t-test results with mean difference, 95% CI, and p-value. Graphical representation of score changes.

Ethical Considerations

Analysis will be performed on anonymized datasets. Results will be reported in aggregate without identifying participants.

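### Both primary outcomes are subjective scores taken by face-to-face interview, and nothing in the plan keeps the interviewer unaware of the arm or separate from the exercise programme

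*Protocol*

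**What the plan says.** The SAP (Variables) names two primary outcomes: "Primary Outcomes: Depression Score (0-27) using PHQ-9 scoring; Anxiety Score (0-21) using GAD-7 scoring". Both are symptom scores built from the patient's own answers, and no objective outcome is listed beside them.

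The protocol (Data Collection Tools and Methods) states: "Data will be collected via face-to-face interviews and patient medical records from the Al Shifa system". The SAP (Data Collection Method) is explicit that this applies to the scales: "Face-to-face interviews for questionnaire administration".

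The protocol (Study Design) describes the arms as "Intervention Group: Receives structured, home-based walking exercise program for 6 months" and "Control Group: Receives standard care without exercise intervention". On follow-up it says: "Post-intervention assessment will be conducted for both groups after 6 months using the same tools". Under Expected Outcomes it gives the direction it anticipates: "The intervention group is expected to show a statistically significant reduction in depression and anxiety scores compared to the control group".

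Neither document mentions blinding or masking, an independent assessor, the interviewer's identity or role, an interview script, or self-completion. The nearest wording is in the SAP (Ethical Considerations): "Analysis will be performed on anonymized datasets". That governs the data after the scores have been recorded.

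**The concern.** When an interviewer reads out questions about mood and worry, tone, prompting, rephrasing and the handling of vague answers can all move the score. If the interviewer knows the arm, that influence can differ between arms. At baseline this is not an issue if the interview precedes allocation. At 6 months it is, because by then the arm is settled and the patient knows it.

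The likely direction is the hypothesised one: lower scores in the exercise arm, through interviewer expectation and through patients wishing to give a welcome answer. Randomisation, intention-to-treat analysis and adjustment for baseline do not correct an error that enters differentially when the outcome is measured. Both primary outcomes pass through the same interview, so both are exposed, and with them the test of hypothesis H2.

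**Working it through.** **Step 1: what the documents establish.**

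| Question | Protocol | SAP |
|---|---|---|
| Are the primary outcomes subjective? | PHQ-9 and GAD-7 | Same scales, named as primary |
| How are they obtained? | Face-to-face interview | Face-to-face interview |
| Can patients be unaware of their arm? | No: exercise versus standard care, no sham or attention control described | Same two groups |
| Is the interviewer masked, independent or scripted? | Not stated | Not stated |
| Is any other stage protected? | Not stated | Anonymised data at analysis only |

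The term open-label appears in neither document. It follows from the design.

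**Step 2: illustration of size.** The plan contains no figure for assessment bias, and no SD or effect size, so there is nothing of its own to reproduce here. Its sample size calculation does not bear on this point.

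Inputs from the SAP: 26 per group analysed, independent t-test on change scores, two-sided alpha 0.05. Assumed: no true effect, and a total assessment bias of *b* SD of the change score.

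- Standard error of the between-arm difference: √(2/26) = 0.277 SD.
- Degrees of freedom: 26 + 26 − 2 = 50. Smallest observed difference reaching p < 0.05: about 0.56 SD.
- Noncentrality: *b* × √(26/2) = *b* × 3.606. The rejection probability comes from the noncentral t distribution with 50 df.

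| Assumed bias *b* (SD) | Noncentrality | Rejects, two-sided | Rejects in favour of exercise |
|---|---|---|---|
| 0 | 0 | 5.0% | 2.5% |
| 0.1 | 0.36 | 6.4% | 5.4% |
| 0.2 | 0.72 | 10.9% | 10.5% |
| 0.3 | 1.08 | 18.6% | 18.4% |
| 0.4 | 1.44 | 29.3% | 29.3% |
| 0.5 | 1.80 | 42.4% | 42.4% |

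Using 27 per arm (all 54 enrolled, split equally) changes little: the two-sided figures for 0.1 to 0.5 SD are 6.5%, 11.1%, 19.1%, 30.3% and 43.8%.

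**Step 3: the same in scale points.** If the SD of the change score were 4 to 6 points (an assumption), 0.56 SD would be about 2.2 to 3.3 points. A bias of 2 points would be 2/4 = 0.50 SD down to 2/6 = 0.33 SD, and alone would give a significant benefit about 42% down to 22% of the time.

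**The case against.** The case on the other side has real weight.

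- *The documents describe no trainer.* The protocol's Intervention section gives only type, duration and frequency of exercise. A reader might infer that the plan has the person who teaches the exercise also score the outcomes. The documents do not say so: they are silent on who does either task. What stands is that nothing prevents the overlap.
- *The scales limit discretion.* They are questionnaires with defined score ranges, not clinician ratings. That reduces the interviewer's room for influence but does not remove it, since no word-for-word reading is required.
- *Patients still know their arm.* A masked interviewer does not touch patients' own expectations. This stands, and it limits what the fix can achieve.
- *The size is assumed.* At 0.1 SD the error rate is 6.4%, close to nominal, and at 0.3 SD the test still does not reject 81% of the time. This also stands: the table shows sensitivity, not evidence of bias in this trial.
- *Stating an expected benefit is not evidence of bias.* Expected Outcomes largely restates H2. It fixes the direction in which any expectation would act, and no more.
- *A separate interviewer may need extra staff.* The documents say nothing about staffing, so this cannot be ruled out. The script, the form and the request to patients do not depend on it.

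**Conclusion.** The concern holds as a risk that the plan leaves open and could cheaply reduce. Both primary outcomes are subjective, an interviewer obtains them after the arm is known to the patient, and the plan neither masks that interviewer nor separates the role from the exercise programme. The bias can run in the hypothesised direction.

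Its size cannot be derived from the documents. On the stated assumptions (26 per arm, no true effect, total bias of 0.1 to 0.5 SD), the nominal 5% test rejects about 6% to 42% of the time. That total combines interviewer influence with patient expectation, so it must not be read as the error that masking would remove.

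A reader might go further and infer that any significant result would be indistinguishable from measurement bias. The documents do not support that: they show an unprotected step, not that bias occurs or is large enough to explain a result. Some risk would in any case remain with a masked interviewer.

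**What to change.** In the protocol (Data Collection Tools and Methods) and the SAP (Data Collection Method), state that:

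1. PHQ-9 and GAD-7 items are read out word for word from a fixed script at baseline and at 6 months.
2. Allocation and any exercise records are kept off the interview form.
3. Patients are asked before the 6-month interview not to mention their arm.
4. Where the existing team allows, the 6-month interviews **in both arms** are done by the same person or people, who have no role in the exercise programme and are not told the arm.
5. Any unblinding is recorded.

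Item 4 should not be met by having two arm-specific collectors exchange patients. One would then interview all exercise patients and the other all controls, which confounds interviewer with arm.

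The SAP already gives a final-analysis count per group, so the interviews may be complete. If so, or if no suitable interviewer exists, report who interviewed and what they knew of the arm. In every case, report the remaining patient-expectation bias as a limitation.

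The cost is a few sentences in each document and some scheduling; items 1 to 3 and 5 need no added staff. The drawback is that blinding is only partial.

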### **Data Analysis Plan**

Data entry and cleaning using SPSS v22; Descriptive statistics for demographics and baseline variables; Baseline comparisons using t-tests or non-parametric equivalents; Paired t-tests for within-group changes; Independent t-tests for between-group differences; Significance set at  $p < 0.05$  (two-tailed).

### **Ethical Considerations**

Ethical approval will be obtained from the Institutional Research and Ethics Committee. Informed consent will be taken from all participants. Confidentiality will be maintained, and participants can withdraw anytime without affecting their treatment.

### **Expected Outcomes**

The intervention group is expected to show a statistically significant reduction in depression and anxiety scores compared to the control group, supporting the integration of home-based exercise programs in dialysis care.

The Effect of Non-Pharmacological (Home-Based Exercise) Intervention on Psychological Distress of Patients Undergoing Hemodialysis at Al Suwaiq Renal Dialysis Center

NCT07083843

Date:15/08/24

Study Objectives

Primary Objective: To evaluate the effect of home-based exercise on reducing psychological distress (depression and anxiety) in patients undergoing hemodialysis.

Secondary Objective: To describe the baseline prevalence and severity of depression and anxiety among hemodialysis patients.

Study Design

Phase I: Cross-sectional assessment of depression and anxiety levels using the University of Michigan Depression Center's tools.

Phase II: Randomized controlled trial (RCT) with intervention and control groups.

Phase III: Post-intervention reassessment after 6 months.

Study Population

Sample size: Initially 132 screened → 54 enrolled → 26 participants per group in final analysis.

Inclusion/Exclusion Criteria: As defined in the study protocol.

Variables

Primary Outcomes: Depression Score (0-27) using PHQ-9 scoring; Anxiety Score (0-21) using GAD-7 scoring.

Independent Variable: Intervention group assignment (Home-based exercise vs. Control).

Covariates: Age, gender, duration of dialysis, comorbidities.

Data Collection Method

Face-to-face interviews for questionnaire administration. Baseline data from Al Shifa system (demographics, clinical history).

Statistical Analysis

- Data Management: Data entry and cleaning in SPSS v22. Descriptive statistics for demographics and baseline variables: Continuous variables: Mean ± SD (or median and IQR if non-normal). Categorical variables: Frequencies and percentages.
- Baseline Comparisons: Independent t-test, Chi-square, or Fisher's exact test for categorical variables.

Main Analysis: Paired t-test for within-group changes; Independent t-test for between-group differences in change scores.

- Significance Level: p-value < 0.05 considered significant; two-tailed tests.

- Handling Missing Data: Intention-to-treat principle; Last Observation Carried Forward method for missing values.

Presentation of Results

Tables for baseline demographics, pre- and post-intervention scores. Paired t-test results with mean difference, 95% CI, and p-value. Graphical representation of score changes.

Ethical Considerations

Analysis will be performed on anonymized datasets. Results will be reported in aggregate without identifying participants.

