## **Hypotheses**

**H1:** There is a high level of psychological distress among patients undergoing dialysis treatment.

H2: Home-based exercise intervention significantly reduces psychological distress (depression and anxiety scores) compared to standard care.

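### The planned change-score t-test is valid but usually less precise than ANCOVA on the baseline score, and the between-group estimate is missing from the results to be reported

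*SAP*

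**What the plan says.** The SAP (Statistical Analysis) sets out: "Main Analysis: Paired t-test for within-group changes; Independent t-test for between-group differences in change scores". No baseline-adjusted model follows. Four covariates are listed under Variables, but no analysis uses them and the baseline score is not among them. The Protocol's Data Analysis Plan says only "Independent t-tests for between-group differences", without saying whether change or 6-month scores are compared.

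Under Presentation of Results the SAP lists "Tables for baseline demographics, pre- and post-intervention scores", then "Paired t-test results with mean difference, 95% CI, and p-value", then graphs of score changes. No between-group estimate appears.

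The question itself is comparative. The second hypothesis reads "Home-based exercise intervention significantly reduces psychological distress (depression and anxiety scores) compared to standard care", the Protocol's second objective is also stated against a control group, and Expected Outcomes says "The intervention group is expected to show a statistically significant reduction in depression and anxiety scores compared to the control group". The SAP gives the analysed size as "26 participants per group in final analysis".

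**The concern.** There are two separate points.

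**Precision.** A change-score t-test is an analysis in which the coefficient of the baseline score is forced to equal 1. ANCOVA estimates it. Both are unbiased under randomisation, but when the true slope is well below 1 the change score carries avoidable baseline noise. With 26 per group, and a sample size derived from a prevalence formula with no power, SD or effect size for the trial comparison, precision should not be given up without a reason.

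**Reporting.** A paired test asks whether one arm changed over time. It absorbs regression to the mean, the passage of time and the effect of attention, so it cannot show that exercise did better than standard care. The only results for which the SAP promises an estimate, interval and p-value are of this kind. A report that followed the list literally could show a significant fall in the exercise arm and leave out the one randomised comparison.

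**Working it through.** **Inputs from the documents.** 26 per arm (SAP, Study Population); two-sided 0.05 (SAP, Significance Level); one follow-up at 6 months with the same tools (Protocol, Study Design). The plan gives no precision or power figure for this comparison, so there is none to reproduce.

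**Assumed inputs, because the documents give none.** Baseline-to-6-month correlation ρ from 0.3 to 0.8; ratio k of the 6-month SD to the baseline SD of 0.8, 1 or 1.25; true difference 0.6 baseline SD. The baseline SD is set to 1.

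**Step 1: is the planned test valid?** Yes. Simulated type I error was between 0.049 and 0.052 for both tests. The comparison is one of efficiency only.

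**Step 2: formulas.**
- Change score: V_C = 1 + k² − 2ρk, t with 50 df.
- ANCOVA: V_A = k²(1 − ρ²) × (1 + 1/48), t with 49 df. Here 1/48 = 1/(2×26 − 4) is the average cost of chance baseline imbalance.
- Standard error of the group difference: √(2V/26).

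Before the small-sample factor, V_C − k²(1 − ρ²) = (1 − ρk)². This is never negative and is zero only when the slope ρk equals 1. With k = 1 the variance ratio is (1 + ρ)/2.

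**Step 3: one case in full (k = 1, ρ = 0.5).** V_C = 1 + 1 − 1 = 1.00; SE = √(2/26) = 0.277; 95% half-width = 2.009 × 0.277 = 0.557 SD. V_A = 0.75 × 1.0208 = 0.766; SE = √(2 × 0.766/26) = 0.243; half-width = 2.010 × 0.243 = 0.488 SD. Variance ratio 0.766.

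**Step 4: equal SDs (k = 1).** Power is from the noncentral t, averaged over chance baseline imbalance.

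| ρ | Variance ratio, ANCOVA to change | Half-width, change / ANCOVA (SD) | Power, change / ANCOVA | Change-score n per group to match ANCOVA at 26 |
|---|---|---|---|---|
| 0.3 | 0.664 | 0.659 / 0.537 | 43% / 60% | 39 |
| 0.5 | 0.766 | 0.557 / 0.488 | 56% / 68% | 34 |
| 0.7 | 0.868 | 0.432 / 0.402 | 78% / 84% | 30 |
| 0.8 | 0.919 | 0.352 / 0.338 | 92% / 94% | 29 |

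**Step 5: unequal SDs.**

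| k | ρ | Slope ρk | Variance ratio | Power, change / ANCOVA |
|---|---|---|---|---|
| 0.8 | 0.3 | 0.24 | 0.513 | 50% / 79% |
| 0.8 | 0.5 | 0.40 | 0.583 | 64% / 86% |
| 0.8 | 0.7 | 0.56 | 0.641 | 84% / 96% |
| 0.8 | 0.8 | 0.64 | 0.653 | 94% / 99% |
| 1.25 | 0.3 | 0.375 | 0.801 | 35% / 42% |
| 1.25 | 0.5 | 0.625 | 0.912 | 46% / 49% |
| 1.25 | 0.7 | 0.875 | 1.001 | 65% / 65% |
| 1.25 | 0.8 | 1.00 | 1.021 | 81% / 80% |

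Simulation with 60,000 trials per setting agrees with these powers to within 0.006.

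**Step 6: where ANCOVA stops helping.** At k = 1 it is ahead up to a slope of 0.957. At k = 1.25 it is slightly worse for slopes between 0.866 and 1.09. At k = 0.8 there is no break-even, since the slope cannot exceed 0.8. The largest loss, at a slope of 1, is 1.0208 × (2.010/2.009)² = 1.022, or 2.2% in expected squared interval width.

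**Step 7: what the paired tests show when there is no treatment effect.** Suppose both arms fall by 0.5 SD (an assumption) and exercise does nothing. In 4,000 simulated trials per setting, the paired t-test in the exercise arm was significant in 54%, 69% and 88% of trials at ρ = 0.3, 0.5 and 0.7. The between-group change-score test rejected in 4.7%, 5.2% and 4.8%. Only the between-group comparison bears on the second hypothesis, and its estimate is not on the reporting list.

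**The case against.** The planned test is a correct, pre-specified between-group test that already uses the baseline score, and no false conclusion follows from keeping it. This stands, and it is why the ANCOVA point is one of efficiency and not an error.

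The gain rests on assumed inputs. With equal SDs and a 0.6 SD effect it runs from 16 power points at ρ = 0.3 to 2 points at ρ = 0.8, and is effectively nil at ρ = 0.9. It also depends on the assumed effect: at ρ = 0.5 it is about 4 points for 0.3 SD, 12 for 0.6 SD and 4 for 1.0 SD. This stands too. The direction is well supported, but the size for this trial is unknown.

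The statement "26 participants per group in final analysis" may describe realised counts. If outcomes by arm are already known, changing the primary test would be post hoc. The documents do not settle this, so the recommendation has to be conditional.

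On reporting, the between-group test is in the Main Analysis, and nothing says that the list is exhaustive. If paired means and intervals are given for both arms, a reader can recover the difference and an interval, because the squared standard errors add. That makes the gap a matter of wording and not a missing analysis. But readers should not have to reconstruct the trial's main result.

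**Conclusion.** The concern holds on both points. The change-score t-test is valid, and ANCOVA on the baseline score is usually more precise. With 26 per group and equal SDs, the ANCOVA variance is 0.66 to 0.92 of the change-score variance for correlations of 0.3 to 0.8. The advantage is larger if scores are less variable at 6 months than at baseline. It is smaller, nil or slightly negative if they are more variable and the slope is near 1. The balance favours ANCOVA: with equal SDs, a possible gain worth 3 to 13 participants per group (29 − 26 to 39 − 26), against a worst loss of about 2% in squared interval width. These figures rest on assumed correlations, SD ratios and effect size.

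The reporting gap is plain on the text and needs no assumption: estimates and intervals are listed for the paired tests only, while the hypothesis is comparative.

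This is a recommended improvement, not a fault that invalidates the plan.

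**What to change.** 1. If outcome data by arm have not been seen, make the primary analysis for each of PHQ-9 and GAD-7 an ANCOVA of the 6-month score on group and baseline score. If they have been seen, keep the change-score t-test as primary and report ANCOVA as supportive. State in the SAP which case applies.
2. In either case, add the between-group difference with 95% CI and p-value, for both scales, to Presentation of Results and name it as the trial result.
3. Keep the paired within-group results if wanted, labelled as descriptive and not as evidence for the second hypothesis.
4. Use the same wording in the Protocol's Data Analysis Plan, so that it says which scores are compared and how.

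Cost: one residual degree of freedom (50 to 49), about 2% in variance for estimating the slope, and text changes in two documents. No new data are needed, since both scores are already collected.

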## **Sample Size and Sampling Technique**

Using Cochran's formula for finite populations, with a total population of 132, a 95% confidence interval, 5% margin of error, and an estimated prevalence of depression of 73%, the calculated sample size is 54 participants.

Sampling Method: Simple random sampling from the list of eligible patients at Al Suwaiq Renal Dialysis Center.

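### Within-arm paired t-tests sit unranked beside the between-group test at the same 0.05 threshold, and nothing says that H2 rests on the between-group test alone

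*SAP*

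**What the plan says.** The hypothesis is comparative. H2 in the protocol's Hypotheses section states: "Home-based exercise intervention significantly reduces psychological distress (depression and anxiety scores) compared to standard care". The second item under the protocol's Objectives also sets exercise against a control group.

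The analysis text does not carry that priority through. The SAP has "Main Analysis: Paired t-test for within-group changes; Independent t-test for between-group differences in change scores", and the threshold for all of it is "p-value < 0.05 considered significant; two-tailed tests". The protocol's Data Analysis Plan gives "Paired t-tests for within-group changes; Independent t-tests for between-group differences", also without order of importance, as items in a general list of methods.

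The SAP's section on presentation of results promises "Paired t-test results with mean difference, 95% CI, and p-value", alongside tables of baseline data and of scores before and after the intervention, and graphs of score change. It does not name the between-group difference, its interval or its p-value.

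There are two primary outcomes: "Primary Outcomes: Depression Score (0-27) using PHQ-9 scoring; Anxiety Score (0-21) using GAD-7 scoring". The SAP expects "26 participants per group in final analysis".

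**The concern.** A paired t-test within one arm asks whether that arm's mean score moved between baseline and 6 months. It contains no information from the other arm. It responds to anything that shifts scores in everyone, such as repeated interviewing, natural course or regression to the mean. It therefore cannot answer H2, however small its p-value.

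Across two outcomes the plan produces four paired tests and two between-group tests, all judged at 0.05, with no statement of which ones decide efficacy. The reporting list then gives prominence to the four that cannot. This leaves room for a familiar misreading: the exercise arm improved significantly, the control arm did not, so exercise works. That contrast is not a test of the difference between arms, and its error rate is not fixed at 5%. What is at stake is the trial's headline conclusion about the walking programme.

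**Working it through.** **The plan's own figure.** The documents state no error rate for this reading, so there is none to reproduce. The only calculated design figure, the sample size of 54, is a prevalence-precision calculation. It contains no effect size, SD or expected change and supplies no input here.

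**Inputs**
- n = 26 per arm (SAP, study population).
- Two-sided 0.05 for every test (SAP, significance level).
- Common standardised mean improvement d, equal in both arms, in units of the SD of the change score. This is *assumed*, because the documents give neither an expected change nor an SD; the range 0 to 0.8 is shown.
- No treatment effect: both arms have the same normal distribution of change and are independent.

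**Step 1. Chance that one arm improves significantly.** The critical value is t(0.975; 25 df) = 2.060. With noncentrality d√26, and √26 = 5.099:

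q = P(noncentral t with 25 df > 2.060).

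**Step 2. Chance of the false reading in favour of exercise.** The exercise arm must improve significantly and the control arm must not. With equal q in both arms and independence, this is q(1 − q).

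| d | d√26 | q | q(1 − q) |
|---|---|---|---|
| 0 | 0 | 0.0250 | 2.4% |
| 0.1 | 0.51 | 0.0709 | 6.6% |
| 0.2 | 1.02 | 0.1638 | 13.7% |
| 0.3 | 1.53 | 0.3125 | 21.5% |
| 0.4 | 2.04 | 0.5004 | 25.0% |
| 0.5 | 2.55 | 0.6882 | 21.5% |
| 0.6 | 3.06 | 0.8365 | 13.7% |
| 0.7 | 3.57 | 0.9291 | 6.6% |
| 0.8 | 4.08 | 0.9749 | 2.4% |

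For example, at d = 0.3: 0.3125 × 0.6875 = 0.2148. The product cannot exceed 0.25, its value at q = 0.5, so 25% is a ceiling for one outcome and not a typical value.

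**Step 3. Simulation check.** With 100,000 simulated trials per scenario, the same reading occurred in 2.5%, 13.5%, 25.2%, 21.4% and 13.7% of trials at d = 0, 0.2, 0.4, 0.5 and 0.6, in agreement with the table.

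**Step 4. The between-group test in the same simulated trials.** The two-sided error was 4.9% to 5.1%, of which about 2.5% favoured exercise, whatever the value of d. At d = 0.4, the within-arm reading favoured exercise while the between-group test did not in 22.8% of trials.

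**Step 5. Two primary outcomes.** At d = 0.4 for both scales, at least one false reading occurred in 32% of simulated trials when the two changes correlate at 0.9, and in 44% when they are uncorrelated. The correlation is also an assumption.

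**Sensitivity to n.** If all 54 enrolled were analysed, 27 per arm, the values at d = 0.2, 0.3, 0.4 and 0.5 would be 14.0%, 21.9%, 25.0% and 20.8%.

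**The case against.** The strongest reply is that the right test is already in the plan. The SAP sentence that names the paired tests also names an independent t-test on change scores, the protocol plans between-group tests too, and H2 points to them. Order in a list is not inferential rank, and the paired tests are labelled accurately as tests of change within a group. This stands: no comparison is missing.

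A reader might infer that the plan declares the paired tests to be tests of H2. Neither document says so. The label Main Analysis appears only in the SAP; the protocol simply lists methods. A reader might also take the protocol's Expected Outcomes section as endorsing the misreading. It does the opposite: it ties support for the programme to a reduction relative to control.

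The reply also holds that 25% is not an error rate of this trial. That is right. It is the peak of a curve for a reading that the plan leaves open and does not adopt, and the curve returns to about 2.4% at both ends of the range. Nor are the q values false positives of the paired test: when both arms truly improve, rejecting the no-change null is correct. The error lies in the inference drawn from it.

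Finally, removing within-arm p-values is partly a matter of reporting style. That is conceded. The sentence fixing the basis for H2 does the essential work.

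What the reply does not remove is the gap itself. No text ranks the tests or calls the paired results descriptive, and the only inferential output promised is the paired one.

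**Conclusion.** The point holds as a gap in priority and reporting. The plan contains the correct test of H2 but does not make it decisive, and its presentation list favours tests that cannot bear on H2.

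The size is conditional. If the split between a significant and a non-significant arm were taken as efficacy when there is no treatment effect, the false reading in favour of exercise would range from about 2.4% to 25% per outcome, and would exceed 13% for common improvements between 0.2 and 0.6 SD of change. The planned between-group test gives about 2.5% in that direction throughout. This rests on 26 per arm, normal and identically distributed changes in the two arms, and an assumed common change.

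A reader might conclude that the trial has a 25% false-positive rate. The documents do not support that: used alone, the between-group test on a single outcome has its nominal 5% error. The correction should be made because it costs almost nothing and settles, before results are read, which comparison decides the conclusion.

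**What to change.** 1. **SAP, Main Analysis, and protocol, Data Analysis Plan.** State that H2 is judged only on the between-group comparison, for PHQ-9 and for GAD-7.
2. **Same two places.** Take the paired t-tests out of the main analysis. Describe within-arm change as mean change with 95% CI by arm, and state that it is not evidence of effectiveness. That statement is needed even without p-values, because a within-arm 95% CI that excludes zero carries the same information as a paired p-value below 0.05.
3. **SAP, presentation of results.** Name the between-group difference with its 95% CI and p-value for each outcome as the inferential result, in place of the paired t-test line.

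The cost is a few sentences in two documents, with no extra patients or data. The only loss is the within-arm p-values, which no stated objective needs: the SAP's primary objective concerns the effect of exercise, and its secondary objective is a baseline description.
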